5.7 Duration of Follow Up

Participants will be monitored closely until they complete the study. Participants who have completed the study will be those that have returned for the final visit and returned all necessary study materials including unused capsules, pill bottle and questionnaires. Participants will be followed for one month by phone after removal from protocol therapy or until death, whichever occurs first. Participants removed from protocol therapy for unacceptable adverse event(s) will be followed until resolution or stabilization of the adverse event.

5.8 Criteria for Taking a Participant Off Study

Participants will be removed from study when any of the following criteria apply:

- Lost to follow-up
- Withdrawal of consent for data submission
- Participant receives any concomitant medication or treatment included in the list in 5.5 describing medications or treatments the participant may NOT receive
- Participant demonstrates an inability or unwillingness to comply with the study regimen and/or compliance requirements
- Participant decides to withdraw from the protocol therapy
- General or specific changes in the participant's condition render the participant unacceptable for further treatment in the judgment of the treating investigator
- Death

The reason for taking a participant off study, and the date the participant was removed, must be documented in the eCRF.

The study team will ensure Off Treatment/Off Study information is updated in OnCore in accordance with DF/HCC policy REGIST-101.

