5. TREATMENT PLAN

5.1 Treatment Regimen

After study registration, eligible participants will be assigned unique study identification numbers. The investigator will contact the MGH Research Pharmacy for drug dispensation. The MGH Research Pharmacy will dispense study capsules, obtained from Amarin Pharma (Bedminster, NJ), containing 0.5-gram of AMR101. The assigned dosage will not change over the course of the study unless dose reduction is indicated (See Section 6). The first dose of the study medication will be given to patients after the initial flexible sigmoidoscopy. Participants will be expected to take 4 capsules orally, twice a day, until the return for their final visit (minimum 8 weeks, maximum 12 weeks). The final visit, 8-12 weeks from the baseline visit, will be scheduled during or before the baseline visit. The MGH Research Pharmacy will assign the participant three bottles of AMR101 each containing 240 capsules (12 weeks, 8 capsules/day) and participants will return any unused capsules and the bottle to the study staff at their final visit. The bottle will be labeled with their participant ID. The participant number must be recorded on the drug dispensation form and in the participants case report form (CRF). These numbers are unique to each participant and must not be re-assigned. Remaining capsules will be counted as a measure of compliance, the number recorded and then the remaining capsules will be immediately destroyed. Weekly calls will be used to monitor adherence and adverse events. Patients who initiate fish oil supplements during the study will be withdrawn and an exit visit performed.

Compliance will be assessed based on drug diary and pills counts, as well as blood measurement of EPA levels. Reported adverse events and potential risks are described in Section 7. No investigational or commercial agents or therapies may be administered with the intent to treat the participants. The principal investigator will review subjects' data periodically throughout the duration of the study for quality, validity and integrity assurance and for adherence to the IRB

approved protocol and will address any data-related issues that might arise.

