5.6 Criteria for Taking a Participant Off Protocol Therapy

Duration of study drug administration will be at minimum 8 weeks and no more than 12 weeks from the initial visit. Duration of administration will equal the number of days between initial and final visit. Study drug administration will continue until the final visit or until one of the following criteria applies:

- Intercurrent illness that prevents further administration of study drug

- Unacceptable adverse event(s)
- Participant demonstrates an inability or unwillingness to comply with the oral medication regimen and/or compliance requirements
- Participant decides to withdraw from the protocol therapy
- General or specific changes in the participant's condition render the participant unacceptable for further treatment in the judgment of the treating investigator
- Participant self-administers any additional non-study fish oil supplements.

Participants will be removed from the protocol therapy when any of these criteria apply. The reason for removal from protocol therapy, and the date the participant was removed, must be documented in the eCRF. Alternative care options will be discussed with the participant.

When a participant is removed from protocol therapy and/or is off of the study, the relevant Off-Treatment/Off-Study information will be updated in OnCore.

In the event of unusual or life-threatening complications, participating investigators must immediately notify the Overall PI, [name] at [contact] or [contact]

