10. STUDY CALENDAR

	Initial Visit	Wk 1	Wk 2	Wk 3	Wk 4	Wk 5	Wk 6	Wk 7	Wk 8	Wk 9	Wk 10	Wk 11	Wk 12	Final Visit ^a
AMR101 Daily		Taken twice daily until final visit												Return unused drugs
Informed consent	X													
Demographics	X													X
Lifestyle Questionnaire	X													X
Nutritional Survey	X													X
Height	X													
Weight	X													
Waist & Hip Circumference	X													

Flexible Sigmoidoscopy	X														X
Tissue Biopsy Specimens Collected	X														X
Blood Samples	X														X
Urine Samples	X														X
Stool Samples	X														X
Drug Diary	X	Used daily until final visit												X	
Drug Compliance Calls ^b		X	X	X	X	X	X	X	X	X	X	X	X	X	
Adverse event evaluation ^b		X	X	X	X	X	X	X	X	X	X	X	X	X	X

a: Final visit will be scheduled during the initial visit and will occur a minimum of 8 weeks and maximum of 12 weeks after the initial visit.
 
b: Once weekly, participants will be contacted by phone to monitor adherence to drug administration and check for adverse events.
															

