13.7 Reporting and Exclusions

Participants who never start protocol therapy or do not return for final flexible sigmoidoscopy and sample collection will be considered inevaluable and will be excluded from all analyses.

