13.7.2 Evaluation of the Primary Efficacy Endpoint

The primary endpoints will be determined for all patients who complete the final flexible sigmoidoscopy and sample collection, regardless of whether the patient complied with study drug use.¹⁴⁴

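### Section 5.8 takes people who stop the drug or comply poorly off study, so some known low takers are likely to miss the final biopsy that the primary analysis needs

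*Combined protocol and SAP*

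**What the plan says.** Section 5.8 lists grounds on which removal from the study is mandatory. Two concern drug-taking: "Participant demonstrates an inability or unwillingness to comply with the study regimen and/or compliance requirements" and "Participant decides to withdraw from the protocol therapy". Neither carries a pill-count, diary or blood EPA threshold.

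Section 5.6, on stopping the drug, also lists withdrawal from therapy. Its non-compliance line is close to that in 5.8 but narrower: "Participant demonstrates an inability or unwillingness to comply with the oral medication regimen and/or compliance requirements".

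On what happens next, section 5.7 says: "Participants will be followed for one month by phone after removal from protocol therapy or until death, whichever occurs first". It adds continued follow-up for people stopped because of adverse events. The study calendar (section 10) has one sigmoidoscopy after baseline: "Final visit will be scheduled during the initial visit and will occur a minimum of 8 weeks and maximum of 12 weeks" after the first. Section 5.1 mentions one other visit, of unspecified content, for one group: "Patients who initiate fish oil supplements during the study will be withdrawn and an exit visit performed".

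On analysis, section 13.7 says that participants who never start therapy or who "do not return for final flexible sigmoidoscopy and sample collection will be considered inevaluable and will be excluded from all analyses". Section 13.7.2 determines the primary endpoint for "all patients who complete the final flexible sigmoidoscopy and sample collection, regardless of whether the patient complied with study drug use".

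**The concern.** Section 13.7.2 signals that poor compliers are meant to count. Section 5.8 directs that those found to be poor compliers leave the study, possibly before the one biopsy that would let them count. The weekly adherence calls (section 5.1) make it realistic to find them before week 8.

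The primary endpoint is the change in mucosal EPA, which should depend on how much drug was taken. Losing known low takers would select on adherence, and the mean among those analysed would sit above the mean among all who were treated. There is no control arm in which the loss would show, and sections 13.5 and 13.7 give no missing-data method or sensitivity analysis for people removed. At stake are the size of the reported change and the population it describes.

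**Working it through.** **Following one participant through the text.** Someone stops capsules at week 4. Under 5.6 they are off therapy, and under 5.8 the same decision takes them off study. Under 5.7 they are phoned for a month, to about week 8, when the final-visit window opens. No section provides a biopsy for them, although none forbids one. Without it, 13.7 excludes them.

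Three groups are not necessarily lost: people stopped for an adverse event or intercurrent illness (in 5.6 but not named in 5.8), people reduced to 2 g/day (section 6), and people whose low intake appears only at the final pill count.

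**Inputs from section 13.2.** Mean change 3.0, SD of the paired difference 9.0, two-sided alpha 0.05, power 80%, 73 evaluable, 10% drop-out, 80 enrolled. Section 13.2 states these for marine omega-3 composition; I use them as the planning figures for the EPA endpoint and read 3.0% as percentage points. Section 8.1.1 gives an EPA half-life of 89 hours.

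**Assumptions, not in the documents.** f is the fraction removed under the two lines: 5% or 10% (10% is the whole drop-out allowance). c is the share of the 3.0-point gain they would have had: 0 or 0.5.

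**Plan's own figure.** The paired t-test with the noncentral t distribution gives n = 73 (power 0.802), as stated. Losing 10% of 80 leaves 72, power 0.797.

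**Shift in the mean.** If those analysed average 3.0, the mean over all treated is 3.0 × (1 − f(1 − c)).

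| f | c | Mean, all treated | Excess in points | Excess, relative |
|---|---|---|---|---|
| 5% | 0.5 | 2.925 | 0.075 | 2.6% |
| 5% | 0 | 2.85 | 0.15 | 5.3% |
| 10% | 0.5 | 2.85 | 0.15 | 5.3% |
| 10% | 0 | 2.70 | 0.30 | 11.1% |

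With c = 1 there is no shift.

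**Against sampling error.** The standard error at n = 72 is 9/√72 = 1.06. The shift is 0.075/1.06 = 0.07 to 0.30/1.06 = 0.28 standard errors.

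**Is c = 0 plausible?** Four weeks off drug is 672 h, and 672/89 = 7.55 half-lives; 2^(−7.55) leaves about 0.5% of drug-derived circulating EPA. Tissue turnover is not given, so this supports a gain near zero in early stoppers but does not establish it.

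**Power if these people are kept (SD 9.0).**
- All 8 planned drop-outs are such removals and have no gain: 80 analysed, mean 72 × 3.0/80 = 2.70, power 0.755.
- 4 of the 8 are, with no gain: 76 analysed, mean 72 × 3.0/76 = 2.84, power 0.776.
- All 8 are, with half the gain: 80 analysed, mean 2.85, power 0.799.

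**Setting the change to 0 for 8 of 80.** Mean 2.70, SD √(0.9 × 81 + 0.09 × 9) = 8.59. Constant zeros shrink the SD below 9.0.

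**The case against.** Much can be said for the plan. Section 5.8 requires a demonstrated inability or unwillingness, not a few missed doses: section 5.3.1 has missed doses skipped, and section 6 keeps people with gastrointestinal complaints on 2 g/day. The study regimen in 5.8 is wider than the oral medication regimen in 5.6 and can cover refusal of visits or biopsies; such people cannot supply the endpoint whatever the rule says. This stands, and is why that line should be narrowed and not deleted.

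The objective in section 1.2 is the effect of daily 4-gram treatment, and the endpoints are mechanistic. For the effect of actually taking 4 g/day, people weeks off drug dilute the answer. That is a fair alternative target, and the plan never names all starters as its population of inference. But an analysis without regard to compliance points the other way, so the upward shift is stated here only relative to all treated participants.

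Section 5.8 also removes users of EPA supplements, through section 5.5, which would tend to lower the mean. The net direction of 5.8 as a whole is therefore not shown; the point concerns the two drug-taking lines.

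A reader might go further and infer any of the following, which the documents do not support:

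- *5.8 and 13.7.2 contradict each other.* Section 13.7.2 is limited to people who complete the final visit, and nothing bars an off-study participant from a biopsy. The conflict is one of effect.
- *The test of zero change is invalid.* If the drug changed nobody's tissue EPA, removing low takers would not create a rise.
- *An overstatement of 11% is to be expected.* That needs every planned drop-out to fall under these two lines with no gain. Section 13.2 gives 10% as general drop-out in endoscopy studies, not as removal for non-compliance.

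**Conclusion.** The point holds, and it is minor. Some low takers identified before the final visit are likely to be missing from the primary analysis set, and relative to all treated participants this tends to raise the mean EPA change. The range of 0.075 to 0.30 points rests on assumed removal rates and assumed lost gain, and is small against sampling error. It also takes tissue EPA to rise less with less drug. What is affected is the estimate and whom it describes. It is still worth correcting before enrolment, because a biopsy not taken cannot be recovered in the analysis.

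**What to change.** 1. In 5.8, delete the line on withdrawing from protocol therapy, and narrow the non-compliance line to people who refuse or cannot undergo study visits, biopsies or sample collection. Poor capsule-taking stays in 5.6 as a reason to stop the drug only. Keep the other 5.8 lines, including the one on medications barred by 5.5, so that nobody who has started an anticoagulant is called back for biopsies.
2. In 5.7, state that participants who stop the drug or take too little of it are invited to the planned 8 to 12 week sigmoidoscopy and sampling, unless they decline or it is unsafe, and are analysed under 13.7.2.
3. Report removals by reason, which the eCRF already records. Add one sensitivity analysis setting the change to 0 for treated participants with a baseline but no final biopsy. Describe it as a no-gain scenario. It is a lower bound on the mean only if the missing group's mean change is not negative, and its reduced SD should not be read as added precision.

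The drafting cost is an edit to two lines, one sentence and one analysis on data already held. The real costs are a somewhat smaller mean, possibly lower power (0.755 at n = 80 and mean 2.70, against 0.797 at n = 72 and mean 3.0), assays on the extra samples, and the burden of the second visit, with up to 24 biopsies, for people no longer on drug. That visit is already planned for every participant, and they may decline it.

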6. DOSING DELAYS/DOSE MODIFICATIONS

Dose reduction will be made as indicated in the following table(s). The descriptions and grading scales found in the revised NCI Common Terminology Criteria for Adverse Events (CTCAE) version 5.0 will be utilized for dose reduction. A copy of the CTCAE version 5.0 can be downloaded from the CTEP website

http://ctep.cancer.gov/protocolDevelopment/electronic_applications/ctc.htm.

When the study staff is informed of a GI-related adverse event, dose reduction may be considered, according to the following dose de-escalation schema.

Dose Level	AMR 101 Dose
Initial Dose	4 grams/day, for the full course of the intervention
Level -1	2 grams/day, for the rest of the intervention period

Criteria for treatment reduction and suggested guidelines for the management of GI toxicities related to AMR 101 are summarized below. These general guidelines may be modified at the discretion of the investigator based on best clinical judgment at that time, but the reason for these reductions must be documented in the medical record. Any GI toxicities related to AMR 101 should be managed according to standard medical practice. These dose reductions are guidance for clinicians for use of this standard therapy.

Participants who report GI-related adverse events including but not limited to the adverse events described in the tables below will be offered dose reduction as well as the option to withdraw from the study.

Nausea	Management/Next Dose for AMR 101
≤ Grade 1	Reduce to dose level -1
Grade 2	Reduce to dose level -1
Grade 3	Reduce to dose level -1
Grade 4	Reduce to dose level -1

Vomiting	Management/Next Dose for AMR 101
≤ Grade 1	Reduce to dose level -1
Grade 2	Reduce to dose level -1
Grade 3	Reduce to dose level -1

Vomiting	Management/Next Dose for AMR 101
Grade 4	Reduce to dose level -1

Diarrhea	Management/Next Dose for AMR 101
≤ Grade 1	Reduce to dose level -1
Grade 2	Reduce to dose level -1
Grade 3	Reduce to dose level -1
Grade 4	Reduce to dose level -1

Constipation	Management/Next Dose for AMR 101
≤ Grade 1	Reduce to dose level -1
Grade 2	Reduce to dose level -1
Grade 3	Reduce to dose level -1
Grade 4	Reduce to dose level -1

Stomach pain	Management/Next Dose for AMR 101
≤ Grade 1	Reduce to dose level -1
Grade 2	Reduce to dose level -1
Grade 3	Reduce to dose level -1
Grade 4	Reduce to dose level -1

7. ADVERSE EVENTS: LIST AND REPORTING REQUIREMENTS

Adverse event (AE) monitoring and reporting is a routine part of every clinical trial. The following list of reported and/or potential AEs (Section 7.1) and the characteristics of an observed AE (Section 7.2) will determine whether the event requires expedited reporting **in addition** to routine reporting.

7.1 Expected Toxicities

AMR101 may produce a hypersensitivity reaction in individuals with known hypersensitivity to shellfish/fish. Because AMR101 contains ethyl esters of omega-3 fatty acid, patients taking other anticoagulants may be at risk to develop a prolonged bleeding time; the risk of active bleeding is unknown.

7.1.1 Adverse Events List(s)

7.1.1.1 Adverse Event List(s) for AMR101

AMR101 is usually well tolerated. According to Micromedex, arthralgia was one of the most commonly reported adverse events associated with the use of AMR101 occurring in 2.3% (14/622) of patients compared with 1% (3/109) in placebo in pooled data from 2 double-blind clinical trials, which included patients with triglyceride values of 200 to 2000 mg/dL. An additional adverse effect from clinical studies was oropharyngeal pain. Mild to moderate GI-related adverse events

that include stomach pain, nausea, loss of appetite, constipation, or diarrhea have also been reported by participants on this and other studies.¹³

7.2 Adverse Event Characteristics

- **CTCAE term (AE description) and grade:** The descriptions and grading scales found in the revised NCI Common Terminology Criteria for Adverse Events (CTCAE) version 5.0 will be utilized for AE reporting. All appropriate treatment areas should have access to a copy of the CTCAE version 5.0. A copy of the CTCAE version 5.0 can be downloaded from the CTEP web site https://ctep.cancer.gov/protocoldevelopment/electronic_applications/docs/CTCAE_v5_Quick_Reference_8.5x11.pdf
- **For expedited reporting purposes only:**
 - AEs for the agent(s) that are listed above should be reported only if the adverse event varies in nature, intensity or frequency from the expected toxicity information which is provided.
 - Other AEs for the protocol that do not require expedited reporting are outlined in the next section (Expedited Adverse Event Reporting) under the sub-heading of Protocol-Specific Expedited Adverse Event Reporting Exclusions.
- **Attribution** of the AE:
 - Definite – The AE *is clearly related* to the study treatment.
 - Probable – The AE *is likely related* to the study treatment.
 - Possible – The AE *may be related* to the study treatment.
 - Unlikely – The AE *is doubtfully related* to the study treatment.
 - Unrelated – The AE *is clearly NOT related* to the study treatment.

7.3 Expedited Adverse Event Reporting

7.3.1 Investigators **must** report to the Overall PI any serious adverse event (SAE) that occurs after the initial dose of study treatment, during treatment, or within 30 days of the last dose of treatment on the local institutional SAE form.

7.3.2 DF/HCC Expedited Reporting Guidelines

Investigative sites within DF/HCC will report AEs directly to the DFCI Office for Human Research Studies (OHRS) per the DFCI IRB reporting policy.

7.3.3 Protocol-Specific Expedited Adverse Event Reporting Exclusions

For this protocol only, the AEs/grades listed below do not require expedited reporting to the Overall PI or the DFCI IRB. However, they still must be reported through the routine reporting mechanism (i.e. case report form).

CTCAE SOC	Adverse Event	Grade	Hospitalization/ Prolongation of Hospitalization	Attribution	Comments
N/A					

7.4 Expedited Reporting to Hospital Risk Management

Participating investigators will report to their local Risk Management office any participant safety reports or sentinel events that require reporting according to institutional policy.

7.5 Routine Adverse Event Reporting

All Adverse Events **must** be reported in routine study data submissions to the Overall PI on the toxicity case report forms. **AEs reported through expedited processes (e.g., reported to the IRB, FDA, etc.) must also be reported in routine study data submissions.**

[figure not shown]
8. PHARMACEUTICAL INFORMATION

A list of the adverse events and potential risks associated with the investigational agent administered in this study can be found in Section 7.1.

8.1 AMR101

8.1.1 Description

The active ingredient of AMR101 is EPA ethyl ester (icosapent ethyl). The molecular formula is $C_{22}H_{34}O_2$, and its molecular weight is 330.51. Its structural formula is:

Icosapent ethyl is de-esterified during absorption into the active metabolite EPA. EPA is absorbed in the small intestine through the thoracic duct lymphatic system into the circulation.

The T_{max} of EPA was about 5 hours following oral administration of icosapent ethyl. EPA is metabolized in the liver by beta-oxidation into acetyl Coenzyme A, which is converted into energy via the Krebs cycle. Cytochrome P450-mediated metabolism is a minor pathway of elimination. The total plasma clearance of EPA at steady state is 684 mL/hr. The elimination half-life of EPA is about 89 hours.

8.1.2 Form

The trial AMR101 (icosapent ethyl) capsules are manufactured and supplied by Amarin Pharma (Bedminster, NJ) as 0.5-gram amber-colored soft-gelatin capsules. The capsules will be ordered by and shipped to the MGH Research Pharmacy where they will be packaged in three pill bottles each containing 240 capsules, which are sufficient for 12-week supply where 8 capsules are taken daily.

